**A POST MARKETING SURVEILLANCE SURVEY OF DYSPORT FOR
EVALUATING SAFETY OF DYSPORT IN KOREAN PATIENTS SUFFERING
FROM SPASTICITY OR DYSTONIA**

SURVEY PROTOCOL
SURVEY number: A-38-52120-114
PRODUCT NAME: Dysport

Final Version 3, Dated: 13th September 2006

Sponsor's Medically Responsible

Person: :

PPD

Ipsen Korea

[name]

[name]

Korea

Tel: PPD

Fax: PPD

**Sponsor's Co-ordinating & Monitoring
Office:**

PPD

Ipsen Korea

[name]

[name]

Korea

Tel: PPD

Fax: PPD

Pharmacovigilance/Emergency contact

PPD

Ipsen Korea

[name]

[name]

Korea

Tel: PPD

Fax: PPD

PROTOCOL SIGNATURES

Investigator Signature:

I have read and agree to the **A POST MARKETING SURVEILLANCE SURVEY OF DYSPORT FOR EVALUATING SAFETY OF DYSPORT IN KOREAN PATIENTS SUFFERING FROM SPASTICITY OR DYSTONIA**. I am aware of my responsibilities as an Investigator under the guidelines of Good Clinical Practice (GCP)¹, local regulations (as applicable) and the survey protocol. I agree to conduct the survey according to these guidelines and to appropriately direct and assist the staff under my control, who will be involved in the survey.

NAME: _____
TITLE: <PRINCIPAL INVESTIGATOR: SIGNATURE: _____

DATE: _____
OFFICE: _____

Full investigational site contact details, including telephone numbers, will be documented in the Trial Master File.

On behalf of the Sponsor:

NAME: PPD _____
TITLE: PPD SIGNATURE: _____
DATE: _____
OFFICE: Ipsen Korea

¹ ICH Harmonised Tripartite Guideline E6: Note for Guidance on Good Clinical Practice (CPMP/ICH/135/95) Step 5, adopted by CPMP July 1996.

SYNOPSIS

Survey Title:	A post marketing surveillance survey of Dysport for evaluating safety of Dysport in Korean patients suffering from Spasticity or Dystonia
Survey Objectives:	To provide a further assessment of the risk/benefit of Dysport as a marketed product
Phase of Trial:	Post Marketing Survey
Survey Design:	Investigators will prescribe Dysport according to their normal practice. Each investigator will record the dose of Dysport administered and the condition being treated. At the patients scheduled return to the site (following visit depends on investigator's judgement, it's usually about 4 weeks later), their treating physician will perform an assessment of safety, and details on any adverse events will be collected. Patients who do not return to site will be contacted by telephone to ask about any adverse events that they have had since their treatment. These data will be recorded on simple Case Record Forms (CRFs) and returned to Ipsen.
Survey Population:	Reports on about 500 patients will be collected.
Survey Treatment:	
Survey Product:
 
The medication under investigation is Dysport®, in unopened vials to be kept at temperatures between 2°C and 8°C
 
DYSPOORT® is presented as a white freeze-dried pellet containing nominally 500 Units of Clostridium botulinum type A toxin-haemagglutinin complex together with 125 µg of human albumin and 2.5 mg of lactose in a clear glass vial.
 
Dysport will be purchased by the centre participating in this post marketing surveillance survey and will be reconstituted at the clinic with sterile physiological saline for injection without preservative according to the SmPC and should be used within eight hours after reconstitution. The treating physician according to the condition being treated will decide the dose and sites of injection, as described in the SmPC.

Survey Evaluations:	
Efficacy Evaluation(s):
 
None
 
Safety Evaluations:
 
Monitoring of adverse events (AEs).
 
Pharmacokinetic Evaluations:
 
None

	Pharmacodynamic Evaluations: None
Statistical Methods:	The sample size of 500 is based on feasibility and not on any statistical considerations. In terms of study reporting, the analysis will be descriptive: data summaries will consist of descriptive statistics like counts, means, standard deviations, medians, minima, maxima or frequencies / percentages as appropriate. The safety analysis will be based on the safety population (defined as all treated patients).

TABLE OF CONTENTS

SIGNATURE PAGE	2
SYNOPSIS.....	3
1. LIST OF ABBREVIATIONS AND DEFINITION OF TERMS.....	8
2. INTRODUCTION.....	9
2.1 Disease Review	9
2.2 Compound Review	9
2.3 Clinical Survey Rationale	9
3. SURVEY OBJECTIVES.....	9
3.1 Primary Survey Objective	9

1. LIST OF ABBREVIATIONS AND DEFINITION OF TERMS

AE	Adverse Event/Experience
CA	Competent Authorities
CDDS	Clinical Development Data Sciences (relates to Sponsor)
CRF	Case Report Form
CRO	Contract Research Organisation
EU	European Union
GCP	Good Clinical Practice
ICH	International Conference on Harmonisation
IEC	Independent Ethics Committee
Survey medication	Investigational Medicinal Product synonymous with “study drug”
IRB	Institutional Review Board
ITT	Intention to Treat
MedDRA	Medical Dictionary for Regulatory Activities
PC	Prostate Cancer
RAP	Reporting and Analysis Plan
SAE	Serious Adverse Event/Experience
SAS®	Statistical Analysis System®
SmPC	Summary of Product Characteristics
SOP	Standard Operating Procedure
SUSAR	Suspected Unexpected Serious Adverse Reactions
TFLs	Tables, Figures and Listings
TEAE	Treatment Emergent Adverse Event
TMF	Trial Master File

2. INTRODUCTION

2.1 Disease Review

Not Applicable (N/A)

2.2 Compound Review

Dysport is the formulation of *Clostridium botulinum* type A toxin-hemagglutinin complex manufactured by Ipsen. It is currently available commercially in over 60 countries. It is registered for the treatment of blepharospasm, hemifacial spasm, cervical dystonia, post stroke arm spasticity, post stroke leg spasticity, cerebral palsy equinus foot spasticity, hyperhidrosis and glabellar wrinkles although not all indications are approved in all countries.

2.3 Clinical Survey Rationale

This is a post marketing survey to collect safety data based on routine treatment of subjects with Spasticity or Dystonia.

3. SURVEY OBJECTIVES

3.1 Primary Survey Objective

To provide a further assessment of the risk / benefit of Dysport as a marketed product.

3.2 Secondary Survey Objectives

none

4. SURVEY DESIGN

4.1 Overview

Centers will prescribe Dysport according to their normal practice. Each center will record the dose of Dysport administered and the condition being treated. At the patients scheduled return to the site (following visit depends on investigator's judgement, it's usually about 4 weeks later), their treating physician will perform an assessment of safety, and details on any adverse events will be collected. Patients who doesn't return to site will be contacted by telephone to ask about any adverse events that they have had since their treatment. These data will be recorded on simple Case Record Forms (CRFs) and returned to Ipsen.

4.1.1 *Population Characteristics*

Patients with Spasticity or Dystonia scheduled to receive Dysport within each participating centre are to be included in this survey.

4.1.2 *Design*

This is an open, non-randomised, multi-centre, non-interventional, post-marketing survey.

4.2 Endpoints

4.2.1 Efficacy Endpoints

None

4.2.2 Safety Endpoints

Collection of adverse events.

4.3 Justification of Design

The aim of the survey is to provide additional risk / benefit information on the use of Dysport within the specifications of the SmPC. The survey is therefore non-interventional, and is designed only to collect data that would normally be available in the standard treatment of patients with Dysport within licensed indications. As such, no additional measures of efficacy or safety are being collected other than those recorded in normal practice.

4.3.1 Survey Duration

The recruitment period will be approximately 4 months. Follow-up of patients will be dependent on each centre's normal practice and the indication treated. The duration of the survey for each subject will be a maximum of 16 weeks (4 months). The overall duration of the survey will be 8 months.

The survey will be considered to have started at first subject inclusion. It will be considered to have finished at normal follow-up visit interval after last Dysport intake.

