6.4 Discontinuation/Withdrawal Procedures

N/A

7. METHODOLOGY**7.1 Survey Schedule**

The schedule of observations and assessments during the survey are summarised below.

Table 1. Schedule of Observations

	Day 0	Follow-up visit	Telephone contact if no follow up visit

Demography& Eligibility	X		
Treatment injections	X		
Adverse events		X	X

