7.2 Survey Visits

7.2.1 *Baseline (Day 0, visit 1)*

All subjects attending the centre for their normal Dysport treatment will receive Dysport as decided by the treating physician, in accordance with the marketing authorisation. The following details will be recorded on the survey CRF:

- Centre number
- Subject number
- Subject initials,
- Demography
- Previous Toxin history
- Indication
- Dysport administration

7.2.2 *Follow-up visit*

Patients will then return for their normal follow up visit and an assessment of safety will be recorded on the CRF along with any AEs that have occurred since the last treatment.

- Collection of adverse events

7.2.3 *Telephone contact*

Contact will be made with the patient by telephone after planned normal follow-up visit, or if the patient is unavailable to visit. Patients will be asked about any AEs that they may have experienced since they received their Dysport treatment. These AEs will be recorded on the CRF.

7.2.4 *Survey Completion or Withdrawal*

N/A

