8.2 Safety Endpoints and Evaluations

8.2.1 *Adverse Events*

AEs will be collected from the first treatment administration to the end of the follow-up period. AEs will be elicited by direct, non-leading questioning or by spontaneous reports. Further details for AE reporting can be found in Section 10.

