10. ADVERSE EVENT REPORTING

An AE is the development of an undesirable medical condition or the deterioration of a pre-existing medical condition following or during exposure to a pharmaceutical product, whether or not considered causally related to the product. An undesirable medical condition can be symptoms (e.g. nausea, chest pain), signs (e.g. tachycardia, enlarged liver) or the abnormal results of an investigation (e.g. laboratory findings, electrocardiogram). In clinical studies an AE can include an undesirable medical condition occurring at any time, including run-in or washout periods, even if no survey treatment has been administered.

This definition includes events occurring from the time of the subject receiving the first administration of Dysport until the end of the survey.

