10.6 Deaths

All AEs resulting in death either during the survey period or within 28 days after the last dose of Survey medication must be reported as an SAE within 24 hours of the Investigator's knowledge of the event.

The convention for recording death is as follows:

- AE term: lead cause of death (e.g. multiple organ failure, pneumonia, myocardial infarction).
- Outcome: fatal.
- The **only exception** is if the cause of death is unknown (i.e. sudden or unexplained death), in which case the AE term may be 'Death' or 'Sudden death'.

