11.4.5 Safety Evaluation

All safety data will be displayed in the subject data listings. Analyses and summary tables will be based upon the safety population.

AEs will be coded according to the Medical Dictionary for Regulatory Activities (MedDRA) and will be classified by MedDRA preferred term and system organ class. AE listings will be presented by subject, system organ class and preferred term.

Incidence of all reported AEs/treatment emergent AEs (TEAE) and SAEs will be tabulated. In addition, summary tables will be presented by maximum intensity, drug relationship and AEs/TEAEs associated with premature withdrawal of survey medication.

A TEAE is defined as any AE that occurs during the active phase of the survey if:

it was not present prior to receiving the first dose of Survey medication, or

it was present prior to receiving the first dose of Survey medication but the intensity increased during the active phase of the survey, or

it was present prior to receiving the first dose of Survey medication, the intensity is the same but the drug relationship became related during the active phase of the survey.

Treatment emergent AEs will be flagged (*) in the AEs listings.

Concomitant medication will be coded by using WHO Drug Dictionary and will be summarised with the number and percentage of subjects receiving concomitant medication by drug class and preferred drug name.

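### The AE percentages have no common time base: follow-up varies up to 16 weeks with no minimum, and the telephone-contact rule is contradictory

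*Protocol*

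**What the plan says.** **Length of follow-up.** Protocol section 4.3.1 lets follow-up vary by site, according to "normal practice and the indication treated. The duration of the survey for each subject will be a maximum of 16 weeks (4 months"). In the synopsis and section 4.1 the visit date is left to the investigator, with about 4 weeks as the usual interval. No minimum and no common cut-off are stated.

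**Analysis.** Section 11.4.5 states: "Incidence of all reported AEs/treatment emergent AEs (TEAE) and SAEs will be tabulated". The denominator is the safety population of section 11.2, meaning everyone with at least one dose. The synopsis lists counts, frequencies and percentages. No fixed window or patient-time measure is mentioned.

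**Telephone contact.** The synopsis and section 4.1 reserve the call for patients who do not come back. Table 1 in section 7.1 heads its column "Telephone contact if no follow up visit". Section 7.2.3 reads: "Contact will be made with the patient by telephone after planned normal follow-up visit, or if the patient is unavailable to visit".

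**AE window.** Section 7.2.2 records "any AEs that have occurred since the last treatment". Section 8.2.1 says "AEs will be collected from the first treatment administration to the end of the follow-up period". Section 10 covers events "from the time of the subject receiving the first administration of Dysport until the end of the survey". Section 11.4.5 defines treatment-emergent events by an active phase of the survey that is not itself defined.

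**The concern.** Sections 4.2.2 and 8.2 make AEs the whole of the evaluation, and section 3.1 sets a risk/benefit assessment as the sole objective. The AE percentage is therefore the main product of the survey. A percentage of patients with an AE means little without the period it covers, because a patient watched for 16 weeks has more time to report an event than one seen at 4 weeks. If the period is set by local habit and by indication, the pooled figure depends on the mix of visit dates as well as on the risk.

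The telephone wording adds to this. A site following section 7.2.3 may contact an attending patient a second time, later and on no stated day. A site following Table 1 will not. The number and timing of AE contacts then depend on which section a site reads. What varies is observation time after an injection on Day 0; the schedule does not show differing drug exposure.

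**Working it through.** **1. Check the cap against the protocol's timeline.** Section 4.3.1 gives recruitment of about 4 months, a subject maximum of 16 weeks (called 4 months) and a total of 8 months. 4 + 4 = 8. In calendar months, 16 × 7 / 30.4375 = 3.68 and 4 + 3.68 = 7.68, which rounds to 8. The 16-week cap is therefore consistent with the timeline, and windows of 4 and 16 weeks differ by a factor of 16/4 = 4.

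**2. How incidence grows with the window.** The protocol gives no AE rate and no AE timing, so both are assumed here. The incidence by week t is F(t) = 1 − exp(−H(t)), where H is the cumulative hazard. Each pattern is set so that F(4) = 10%, that is H(4) = −ln(0.90) = 0.1054.

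- Constant hazard: F(t) = 1 − 0.90^(t/4).
- Hazard halving every 2 weeks: H(t) = A(1 − 2^(−t/2)). Since 1 − 2^(−2) = 0.75, A = 0.1054/0.75 = 0.1405. Then F(16) = 1 − exp(−0.1405 × 0.9961) = 13.1%.
- All AEs within 4 weeks: F(t) = 10% for every t from 4 weeks on.

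| Pattern | 4 weeks | 8 weeks | 16 weeks | Ratio 16:4 |
|---|---|---|---|---|
| Constant hazard | 10.0% | 19.0% | 34.4% | 3.4 |
| Halving every 2 weeks | 10.0% | 12.3% | 13.1% | 1.3 |
| All within 4 weeks | 10.0% | 10.0% | 10.0% | 1.0 |

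For other assumed 4-week risks under a constant hazard, 2% becomes 7.8%, 5% becomes 18.5% and 20% becomes 59.0% at 16 weeks (ratios 3.9, 3.7 and 3.0).

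**3. Effect on the pooled percentage.** Suppose some patients are followed for 16 weeks and the rest for 4. The split is an assumption.

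| Share followed 16 weeks | Constant hazard | Halving every 2 weeks | All within 4 weeks |
|---|---|---|---|
| 0% | 10.0% | 10.0% | 10.0% |
| 20% | 0.8 × 10.0 + 0.2 × 34.4 = 14.9% | 0.8 × 10.0 + 0.2 × 13.1 = 10.6% | 10.0% |
| 50% | 0.5 × 10.0 + 0.5 × 34.4 = 22.2% | 0.5 × 10.0 + 0.5 × 13.1 = 11.5% | 10.0% |

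In the constant-hazard column the underlying rate is the same in every row: 0.1054/4 = 0.0263 per week, or 2.63 per 100 patient-weeks. Only the follow-up mix changes.

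**4. Telephone rules side by side.** Take a patient who attends at week 4. Under the synopsis, section 4.1 and Table 1, that visit is the last AE contact. Under section 7.2.3 a call may follow, with no day given, and the window runs on to that call. For a patient who does not attend, all the passages lead to a call, but none fixes its date.

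**5. Window wording.** Table 1 places injections on Day 0 only, and section 11.4.5 anchors treatment-emergent events to the first dose of survey medication. The first and the last treatment therefore coincide unless a patient is re-injected during follow-up. The start wording is loose but rarely matters. The end is the subject's last contact under any practical reading, but no section says so.

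**The case against.** The case for leaving the plan alone has four parts.

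- **Detail belongs elsewhere.** Section 11.4 refers the detailed analysis to a separate reporting and analysis plan, which is not at hand and could add fixed-window or patient-time summaries. That is fair, and it means the absence of any time adjustment is inferred from the protocol's wording. But such a plan cannot settle conflicting site instructions or define the collection window after the fact.
- **Variable follow-up is deliberate.** Section 4.3 restricts the survey to what normal practice yields. This stands. It argues against imposing a fixed visit or extra calls, and against dropping treated patients from the denominator. It does not argue against reporting the follow-up time that was observed.
- **The survey is descriptive.** Section 11.3 disclaims definitive conclusions, no testing is planned, and section 11.5 plans no subgroup analysis. No error rate is at stake, and the harm is limited to how the percentages can be read.
- **Section 7.2.3 may mean only that the call comes once the planned visit date has passed without attendance.** That reading is possible, but the text does not say so.

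A reader might also infer more than the documents support:

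- That section 10 reaches back to Dysport given before the survey. Table 1 and the first-dose anchor in section 11.4.5 make this strained.
- That the end of the survey and the end of follow-up are truly different dates. For a single subject they can be the same point, since section 4.3.1 ends the survey at the normal follow-up interval after the last Dysport.
- That section 10.6, with its period "within 28 days after the last dose of Survey medication", requires active contact to day 28. It is a reporting duty triggered by the investigator's knowledge of the event, so a visit before day 28 does not breach it.

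**Conclusion.** The point holds in two parts. The pooled AE percentage has no common time base, because observation time varies by centre and indication from an unstated minimum to 16 weeks. The telephone rule in section 7.2.3 does not match the synopsis, section 4.1 or Table 1.

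The size cannot be fixed from the protocol. With an assumed 10% incidence at 4 weeks, the 16-week figure lies between 10% and 34%, depending wholly on how early AEs occur. The 3.4-fold ratio should not be read as the expected distortion: it needs a hazard that stays constant for 16 weeks after one injection, and it compares the usual visit with the cap. It would also go too far to say that visit habits drive the result as much as the product does, since the distribution of visit times is unknown. The defect deserves correction because it concerns the only endpoint and is cheap to repair.

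**What to change.** 1. Reconcile section 7.2.3 with the synopsis, section 4.1 and Table 1 so that one telephone rule applies at every site.
2. State one AE window, from the Day 0 survey injection to the subject's last contact, and use it in sections 7.2.2, 8.2.1, 10 and 11.4.5. Replace or define the active phase in section 11.4.5 accordingly.
3. Keep the incidence on all treated subjects. Beside it, give AE incidence at day 28 by Kaplan-Meier in the full safety population, censored at last contact, and AE events per patient-month with the distribution of follow-up time. The Kaplan-Meier figure assumes that the timing of last contact is unrelated to AE risk. Centre and indication could affect both, so the report should say this.
4. Make sure AE onset date and contact date are on the CRF. The form is not shown and may already hold them; section 13.3 already requires visit dates and AEs in the source documents.

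The cost is some protocol wording, a little more analysis and at most one or two date fields. Treated patients stay in the denominator, and no patient contact beyond normal practice is needed.

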5. COMPLIANCE WITH GOOD CLINICAL PRACTICE, ETHICAL CONSIDERATIONS & INFORMED CONSENT

5.1 Compliance with Good Clinical Practice and Ethical Considerations

NA.

According to Korea Food Drug Administration (KFDA) guideline, the followings are not the scope of clinical trial approval of KFDA. Therefore Compliance with Good Clinical Practice and Ethical Considerations are not applicable for Post marketing surveys based on Korean regulation.

- Studies for investigation of adverse event and observation of clinical efficacy of the already-marketed product with the already – approved label.
- Studies of the already-marketed product not for safety and efficacy data collection or not for commercial use
- Studies of the already-marketed product for developing the treatment of life-threatening disease which has no standard therapy nor alternative therapy
- Studies of In-Vitro diagnostics or quasi-drug
- Studies of the already marketed drug with other cases which KFDA commissioner admits.

*Pharmaceutical affairs act reinforcement regulations (amended at 2005 Jun 8)

5.2 Informed Consent

NA

Refer to section 5.1

6. SURVEY POPULATION**6.1 Subject Identification Code List and Number of Subjects**

Each Investigator will maintain a record of all subjects enrolled into the survey.

This record called Subject Identification Code List should be kept confidential at the survey centre and should contain the centre number, subject number, subject name, subject initials, and telephone number.

It is planned to recruit approximately 500 subjects in approximately 20 centres in Korea.

6.2 Inclusion Criteria

All subjects must fulfil the following:

- 1) Subjects with indication disease scheduled to receive Dysport as per normal treatment practice, and in respect with Dysport SmPC.
- 2) Adult or child over the age of 2 years

6.3 Exclusion Criteria

Subjects will not be included in the survey if :

- 1) Subject has hypersensitivity to Dysport or drugs with a similar chemical structure.
- 2) Treatment with any other investigational drug within the last 30 days before survey entry.

